#### 8.3.3. Demographics and Medical History

Patient's demographic data and medical history will be reviewed and documented at the time point(s) specified in Table 4. Tumor measurements should be collected prior to the patient's enrollment on the study. Measurements to collect should include any measurements RECIST made during the patient's previous treatment with an anti-PD-(L)1 agent.

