with the longest diameter), be representative of all involved organs, but in addition should be those that lend themselves to reproducible repeated measurements. It may be the case that, on occasion, the largest lesion does not lend itself to reproducible measurement; in such circumstance, the next largest lesion which can be measured reproducibly should be selected. A sum of the diameters (longest for non-nodal lesions, short axis for nodal lesions) for all target lesions will be calculated and reported as the baseline sum diameters. If lymph nodes are to be included in the sum, then only the short axis is added into the sum. The baseline sum diameters will be used as a reference to further characterize any objective tumor regression in the measurable dimension of the disease.

Non-target lesions: All other lesions (or sites of disease) including any measurable lesions over and above the 5 target lesions should be identified as non-target lesions and should also be recorded at baseline. Measurements of these lesions are not required, but the presence, absence, or rare cases of unequivocal progression of each should be noted throughout follow-up.

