## 8.3.10.4. Response Criteria

#### Evaluation of Target Lesions

CR: Disappearance of all target lesions. Any pathological lymph nodes (whether target or non-target) must have reduction in short axis to <10 mm.

PR: At least a 30% decrease in the sum of the diameters of target lesions, taking as reference the baseline sum diameters.

PD: At least a 20% increase in the sum of the diameters of target lesions, taking as reference the smallest sum on study (this includes the baseline sum if that is the smallest on study). In addition to the relative increase of 20%, the sum must also demonstrate an absolute increase of at least 5 mm. (NOTE: the appearance of one or more new lesions is also considered progression).

SD: Neither sufficient shrinkage to qualify for PR nor sufficient increase to qualify for PD, taking as reference the smallest sum diameters while on study.

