#### **13.4.1.** Primary Efficacy Endpoints Analysis

Primary efficacy analysis will be evaluated in patients in the Efficacy Evaluable population for each group separately and overall. The objective improvement rate (as defined in Section 11.1) after continued anti-PD-1 therapy with ALKS 4230 will be summarized by group (Group 1 and Group 2) separately and overall with descriptive statistics. The analysis of objective response rate using an exact binomial test will also be conducted separately for each group.

The 95% CI on the objective improvement rate will be reported. Similar approaches will also be applied to the overall population.

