3. DATA ANALYSIS

3.1. General Statistical Methodology

Baseline for efficacy or safety analysis is defined as the last non-missing assessment before the first dose of study drug in ION-01-ALKS 4230 study on Day 1, and it will be used for all efficacy and safety analysis unless specified otherwise.

In general, summary statistics (n, mean, standard deviation, median, minimum and maximum for continuous variables, and number [%] of patients in each category for categorical variables) will be provided by group for all variables. Time-to-event variables will be summarized by Kaplan-Meier plots, medians, and ranges. The data will be tabulated and analyzed with respect to patient enrollment and disposition, demographic and baseline characteristics, prior and concomitant medications, efficacy, and safety measures. Source data for the summary tables and statistical analyses will be presented as patient data listings. All statistical tests and CIs, unless stated otherwise, will be 2-sided and will be set at α =0.05.

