3.11.2. Efficacy Analysis for the Primary Efficacy Endpoint

The primary efficacy endpoint is the rate of new or improved antitumor response (hereafter referred to as objective improvement) after the addition of ALKS 4230 treatment in patients receiving ongoing anti-PD-1 therapy but who have not achieved a CR.

An objective improvement for patients within Group 1 (Cohorts 1 and 2) is defined as:

- SD at screening that improves to PR or CR,
- PR at screening that improves to CR

An objective improvement for patients within Group 2 (Cohorts 3 and 4) is defined as:

• PD at screening that improves to PR or CR

Primary efficacy analysis will be evaluated in patients in the Efficacy Evaluable population for each group separately and overall. The objective improvement rate after continued anti-PD-1 therapy with ALKS 4230 will be summarized by group (Group 1 and Group 2) separately and overall with descriptive statistics.

Objective improvement rate for Group $1 = \frac{\text{number of patients who achieved CR or PR}}{\text{number of patients in Group 1}}$

Objective improvement rate for Group $2 = \frac{\text{number of patients who achieved CR or PR}}{\text{number of patients in Group 2}}$

The analysis of objective improvement rate using an exact binomial test will be conducted separately for each group. The two-sided 95% confidence interval (CI) on objective improvement rate will be estimated by Clopper-Pearson method.

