5. CHANGES IN CONDUCT OR PLANNED ANALYSES FROM THE PROTOCOL

There are no changes made to the statistical methods specified in the ION-01-ALKS 4230 study protocol (dated 29 Dec 2018).

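### SAP 3.11.2 defines Group 1 improvement one way and computes it another: the formula counts any CR or PR, although a patient already in PR at screening must reach CR, so the primary rate can be overstated.

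*SAP*

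**What the plan says.** SAP 3.11.2 first sets out objective improvement by disease status at screening. In Group 1, SD has to become PR or CR (Cohort 1), and for Cohort 2 the requirement is "PR at screening that improves to CR". In Group 2, PD has to become PR or CR. The same definition stands in SAP 1.3.1 and Protocol 11.1.

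SAP 3.11.2 then writes the rate as a fraction for each group. Both numerators read "number of patients who achieved CR or PR", and the denominators are all patients in Group 1 and in Group 2. Neither fraction refers to screening status. An overall rate is also planned, but no formula is given for it.

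Protocol 13.4.1 gives no fraction. It refers back to the definition: "The objective improvement rate (as defined in Section 11.1"). SAP 5 states: "There are no changes made to the statistical methods specified in the ION-01-ALKS 4230 study protocol". The one revised definition listed in SAP 5.1 is the Efficacy Evaluable Population.

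**The concern.** This is the primary endpoint, and one section of the SAP supports two different numerators for one of its two reporting groups. Group 1 contains Cohort 2, whose patients are already in PR when they enrol. If the fraction is programmed as printed, a Cohort 2 patient with PR on study counts as improved. Under the definition that patient has not improved. The Group 1 rate would then include patients whom the plan itself classes as failures, and so would the overall rate if it uses the same numerator. The study is open-label and single-arm, so leaving the choice open also means that it could be made after the responses are known.

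**Working it through.** There is no planned figure to reproduce: the group sizes are not visible and the point concerns two text rules. The check sets the rules side by side, finds the patients on whom they disagree, and sizes the effect under stated assumptions.

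**Step 1. Compare the rules (SAP 3.11.2).**

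| Status at screening | Best result on study | Definition | Formula |
|---|---|---|---|
| SD (Cohort 1) | PR or CR | counted | counted |
| PR (Cohort 2) | CR | counted | counted |
| PR (Cohort 2) | PR, not CR | **not counted** | **counted** |
| PD (Cohorts 3 and 4) | PR or CR | counted | counted |

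They differ in one row. The formula's numerator always contains the definition's numerator, so the difference is never negative. For Group 2 the two agree.

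**Step 2. Who falls in that row.** Protocol 8.3.10.4 defines PR as "At least a 30% decrease in the sum of the diameters of target lesions, taking as reference the baseline sum diameters". Protocol 8.3.10.2 adds: "The baseline sum diameters will be used as a reference to further characterize any objective tumor regression". SAP 3.1 fixes the time point: "Baseline for efficacy or safety analysis is defined as the last non-missing assessment before the first dose of study drug". Read together, on-study PR is measured from the scan before the first study dose, not from the scan before earlier anti-PD-(L)1 therapy.

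Example with assumed sums: 100 mm before prior therapy, 65 mm at study baseline (65/100 − 1 = −35%, hence PR at entry).
- On study 65 mm: 65/65 − 1 = 0%, which is SD. Counted by neither rule.
- On study 45 mm: 45/65 − 1 = −30.8%, which is PR. Counted by the formula only.

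So merely holding the earlier PR does not trigger the conflict. A further decrease of at least 30% that stops short of CR does.

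**Step 3. Size of the excess.** Let n₁ be the number of patients in Group 1 and k the number of Cohort 2 patients with on-study PR but not CR. The excess is k/n₁ = s × q, where s is Cohort 2's share of Group 1 and q is the share of Cohort 2 with such a PR. Neither s nor q is given, so both are assumptions. Excess in percentage points:

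| s | q = 5% | q = 10% | q = 20% |
|---|---|---|---|
| 20% | 1.0 | 2.0 | 4.0 |
| 50% | 2.5 | 5.0 | 10.0 |
| 65% | 3.25 | 6.5 | 13.0 |

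**Step 4. Effect on the reported result.** Assume n₁ = 20, with 10 in Cohort 2, two SD patients who improve and no Cohort 2 patient who reaches CR. Intervals are two-sided 95% Clopper-Pearson, as SAP 3.11.2 specifies.

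| k | Rate | 95% CI |
|---|---|---|
| 0 (equals the definition) | 2/20 = 10% | 1.2% to 31.7% |
| 1 | 3/20 = 15% | 3.2% to 37.9% |
| 2 | 4/20 = 20% | 5.7% to 43.7% |

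**Step 5. Dependence on the reference scan.** If PR were scored against the scan before prior therapy, the 65 mm patient above would be PR at −35%, and the formula would count every Cohort 2 patient who simply stays in PR. In the same assumed group, k could reach 10, giving 12/20 = 60% (36.1% to 80.9%) against 10%. No text provides for that reference. However, Protocol 8.3.3 collects the RECIST measurements made during prior anti-PD-(L)1 treatment without saying how they will be used.

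**The case against.** The best reply is that the left side of the fraction is the objective improvement rate, a term defined a few lines above, so the numerator is shorthand under a controlling definition. Programming specifications and mock tables are separate documents and may already apply it. In addition, Protocol 13.4.1 names the objective response rate as the quantity for the exact binomial test, and the endpoint sentence speaks of new or improved response. A Cohort 2 patient going from 65 to 45 mm could be said to have a new response. Finally, the study estimates a rate descriptively with no visible decision threshold, and response is also reported by cohort and in listings, so any extra PR could be traced.

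Part of this stands. The definition should govern, literal programming is a risk rather than a certainty, the size cannot be fixed from the documents, and the effect may be zero.

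The rest does not remove the conflict. The formula does not say that it is conditional on screening status, and its wording for Group 1 is identical to Group 2, where it is correct. The endpoint sentence is made specific by the definition that follows it, which requires CR after PR. The SAP changed the protocol's response-rate wording for the exact test to objective improvement rate, so that wording does not support the formula. The confirmatory scan in Protocol 8.3.10 and SAP 1.3.1 is called for on conversion from PD or SD to PR, or from PR to CR. Those are the definition's transitions, and the formula's extra patients are not among them. Cohort tables would let a reader detect the error but would not correct the primary rate.

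**Conclusion.** The concern holds. For Group 1, the formula in SAP 3.11.2 contradicts the definition in the same section, in SAP 1.3.1 and in Protocol 11.1, and it is not declared as a change. Programmed literally, it can only raise the Group 1 rate, by k/n₁. Over assumed values of s from 20% to 65% and q from 5% to 20%, the excess is 1.0 to 13.0 percentage points; at s = 50% and q = 10% it is 5.0 points. If no Cohort 2 patient has a further decrease of at least 30% short of CR, the rules give the same answer. These figures assume that PR is scored against the study baseline. The conclusion that the formula is wrong as written depends on none of them. Because it concerns the primary endpoint, it should be corrected before the SAP is final.

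**What to change.** In SAP 3.11.2, replace the Group 1 numerator with: number of patients with SD at screening who reach PR or CR, plus number of patients with PR at screening who reach CR. Leave the Group 2 numerator as it is. Define the overall numerator as the sum of the two group numerators.

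Two clarifications belong in the same edit, although the correction does not rest on them. State that Cohort 2 is scored against the study baseline sum, which is where Protocol 8.3.10.2 and 8.3.10.4 and SAP 3.1 already point. State also that PR and CR here mean responses confirmed by the 6-week scan, as the note to Protocol Table 8 sets for this trial.

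The cost is a wording change to one formula before database lock, with no new data. Compared with the literal formula, the reported rate can only fall or stay the same.

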3.11.3. Efficacy Analysis for the Secondary Efficacy Endpoints

Secondary efficacy endpoints in this study include:

- DOR, PFS, TTP, rate of non-progression at 6 months, and OS
- Antitumor response rate of subsets of patients based on disease status (PR, SD, or PD) at screening
- Antitumor activity as measured by radiological assessment compared to screening

The efficacy analysis for the secondary endpoints will be performed for the following endpoints.

• Duration of Response:

Duration of response (DOR) is defined as the time from the first documentation of response CR or PR (whichever is first recorded) to the first documentation of objective tumor progression or death due to any cause. Patients who are alive and progression free on the analysis cut-off date will be censored at their last evaluable tumor response assessment before initiation of any new anticancer treatment.

Patients with 2 or more consecutive missing response assessments prior to death or a visit with documented progression will be censored at the last date of tumor assessment when the patient was documented to be progression free. The detailed censoring rules for DOR is in section 6.2.3.

DOR will be calculated as follows (in weeks):

(date of disease progression/death – date of first response (CR or PR) + 1)/7

The distribution of DOR will be estimated using Kaplan-Meier methodology. The median point estimate DOR will be provided along with the two-sided 95% CIs based on the Efficacy Evaluable population. Kaplan-Meier curves will be provided.

• Progression-Free Survival:

Progression-free survival (PFS) is defined as the time from the first dose to the first documentation of objective tumor progression, start of alternate therapy or death due to any cause. Patients who do not have disease progression or have not died will be censored at the last known time that the patient was progression free. If a patient begins a new anticancer treatment (either systemic or local) prior to documented progression or death, or if a patient is removed from the study due to undocumented clinical disease progression, then the patient will be censored at the last assessment where the patient was documented as progression free prior to the intervention. Patients with 2 or more consecutive missing response assessments prior to a visit with documented progression (or death) will be censored at the last date of tumor assessment when the patient was documented to be progression free. The detailed censoring rules for PFS is in section 6.2.2.

Progression-free survival will be calculated as follows (in weeks):

(date of disease progression/death – first dose date +1)/7

The survival distribution of PFS will be estimated using Kaplan-Meier methodology. The median PFS will be provided along with the two-sided 95% CIs based on the Efficacy Evaluable population. In addition, Kaplan-Meier curves will be provided. The 6-month PFS rate will be estimated using the Kaplan-Meier estimate.

• Time to Progression:

Time to progression (TTP) is defined as the time from the first dose to the confirmed tumor progression. All events of disease progression will be included regardless of whether the patient discontinued the study drug. If the patient has not experienced disease progression, the patient's data will be censored at the date of last disease assessment. Data for patients without any disease assessments performed after the first dose will be censored at the date of first study drug.

The TTP will be calculated as follows (in weeks):

(date of disease progression – date of first dose + 1)/7

TTP will be analyzed by Kaplan-Meier methodology. Median TTP will be calculated and 95% confidence interval for median TTP will be presented.

• Overall Survival:

Overall survival (OS) is defined as the time from the first dose to death due to any cause. For patients without documentation of death, patients will be censored at the date that the patient was last known to be alive or the date of study cutoff, whichever comes earlier. The detailed censoring rules for OS is in section 6.2.1.

OS will be calculated as follows (in weeks):

(date of death/censoring - date of first dose date + 1)/7

OS will be analyzed by Kaplan-Meier methodology. Median OS will be calculated and 95% confidence interval for median OS will be presented. In addition, Kaplan-Meier curves will be provided. The one-year OS rate will be estimated using the Kaplan-Meier estimate.

In addition, the objective response rate will be summarized for each of the 4 cohorts, and the percentage change from baseline in target lesions will be summarized by group and overall.

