#### 8.3.10.6. Duration of Response

Duration of overall response: The duration of overall response is measured from the time measurement criteria are met for CR or PR (whichever is first recorded) until the first date that recurrent or PD is objectively documented (taking as reference for PD the smallest measurements recorded since the treatment started).

The duration of overall CR is measured from the time measurement criteria are first met for CR until the first date that PD is objectively documented.

Duration of SD: The duration of SD is measured from the start of the treatment until the criteria for progression are met, taking as reference the smallest measurements recorded since the treatment started, including the baseline measurements.

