1.2. Summary of the Study Design

The study will assess the antitumor efficacy of ALKS 4230 in combination with pembrolizumab in patients with advanced, recurrent, and/or HNSCC on treatment with an anti-PD-(L)1 antibody (pembrolizumab or nivolumab) without having achieved a CR.

The study is a multi-center, Phase 2, open-label therapy study in collaboration with ION. Patients must have received anti-PD-(L)1 therapy prior to enrollment into the study. After enrollment in the study, ALKS 4230 with pembrolizumab will be administered to 4 cohorts of patients with advanced, recurrent, and/or metastatic HNSCC who have received anti-PD-(L)1 therapy whose current response is as follows:

- Cohort 1: SD, defined as ≥ 12 weeks of SD per RECIST criteria
- Cohort 2: PR with no further reduction in tumor size or response for ≥8 weeks (ie, PR and not improving further)
- Cohort 3: PD with no prior response to anti-PD-(L)1 therapy after ≥8 weeks on anti-PD-(L)1
- Cohort 4: Current PD after prior achievement of best response of SD or PR and after ≥8 weeks on anti-PD-(L)1 therapy

Patients will be administered the combination of ALKS 4230 and pembrolizumab. For simplification, the 4 cohorts of patients will be combined into 2 arms:

- Group 1 will consist of all patients with current SD or PR (Cohorts 1 and 2) who are not progressing or further demonstrating reductions in tumor size.
- Group 2 will consist of patients with PD (Cohorts 3 and 4).

Baseline tumor biopsy will be required at the time of study entry after screening procedures have been completed and prior to first administration of combination regimen to assess each patient's tumor characteristics in an effort to identify patients with tumors that may have limited pembrolizumab efficacy or potential response to anti-PD-1/ALKS 4230 combination. Tumors will be assessed for quantity and character of tumor-infiltrating T cells and other leukocytes, and for quantitative assessment of PD-L1 expression, gene signatures that correlate with response or lack of response Patients will also have a post-treatment (second) biopsy at C1D12, or at any time from C1D8 through C1D19, to assess whether the addition of ALKS 4230 to the treatment regimen alters the TME and what changes on therapy (immunopharmacodynamics) predispose to responses to the combination.

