6.2.1. Censoring Rules for Duration of Response (DOR)

The Duration of Response censoring dates for a patient is in Table 4. The Start date: the date of first documentation of response (CR or PR).

Table 4:	Censoring Rules for Duration of Response
----------	---

Situation	Date of Progression or Censoring	Outcome
No baseline or unreadable baseline assessment, but readable post-baseline assessments	Date of the 1 st dose of the study drug	Censored
Progression documented between scheduled visits	 Earliest of Date of radiological assessment showing new lesion (if progression is based on new lesion); or Date of last radiological assessment of measured lesions (if progression is based on increase in sum of measured lesions) 	Progressed
Death before first PD assessment	Date of death	Progressed
Death between adequate assessment visits	Date of death	Progressed
Treatment discontinuation for undocumented progression	Date of last tumor assessment with no documented progression	Censored
Treatment discontinuation for toxicity of other reason	Date of last tumor assessment with no documented progression	Censored
Patients still on treatment without PD as of data cut-off	Date of last tumor assessment	Censored
Treatment discontinuation for other than PD or death with post-baseline tumor assessments	Date of last tumor assessment	Censored
New anticancer treatment started before PD or death	Date of last tumor assessment before start of new treatment	Censored
Death or PD after two or more missed tumor assessments	Date of the last tumor assessment before missed assessments	Censored
Only NE assessments after CR, PR, SD	Date of last tumor assessment before NE assessments	Censored

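### Duration of response starts at any first CR or PR, so for some patients who enter in PR it begins before, or exists without, the CR that counts as their objective improvement

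*SAP*

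**What the plan says.** **DOR start.** Three places give the same rule, with no exception by cohort:

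- SAP 3.11.3 counts "the time from the first documentation of response CR or PR (whichever is first recorded"), and its formula subtracts the "date of first response (CR or PR").
- SAP 6.2.1 (DOR censoring rules, Table 4) gives the start as "the date of first documentation of response (CR or PR").
- Protocol 8.3.10.6 has DOR "measured from the time measurement criteria are met for CR or PR (whichever is first recorded").

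**Who is in the analysis.** SAP 3.11.3: "The median point estimate DOR will be provided along with the two-sided 95% CIs based on the Efficacy Evaluable population". It is not limited to patients with objective improvement. The only exclusion stated is in protocol 13.4.2, for missing response data.

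**Cohort 2.** SAP 1.2 describes its patients as having "PR with no further reduction in tumor size or response for ≥8 weeks". For them SAP 3.11.2 lists one qualifying change, "PR at screening that improves to CR"; protocol 11.1 agrees. In Cohorts 1, 3 and 4, either PR or CR qualifies.

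**The concern.** The study has its own definition of response, objective improvement, and Cohort 2 is the one cohort in which a PR does not meet it. DOR uses PR as a start in that cohort all the same. A reader will take DOR as the durability of the response reported in the primary analysis. For Cohort 2 it may instead measure time from a different, earlier event, or add patients who had no objective improvement by the bulleted definition. Protocol 13.4.2 reports DOR by group and overall, so this carries into both the Group 1 and the overall summary.

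**Working it through.** The documents give no DOR figure to reproduce. The check applies the SAP's own formula to illustrative Cohort 2 records. All event days and tumor sums below are assumptions.

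**Formula (SAP 3.11.3):** DOR in weeks = (date of progression or death − date of first response + 1)/7.

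**1. PR, then CR.** PR at day 43, CR at day 85, progression at day 211.
- SAP rule: (211 − 43 + 1)/7 = 169/7 = 24.1 weeks.
- From the objective improvement (CR): (211 − 85 + 1)/7 = 127/7 = 18.1 weeks.
- Excess: 42/7 = 6.0 weeks, or 42/127 = 33%.

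The excess always equals the PR-to-CR interval. With PR at week 6 and progression at week 48, the SAP gives 42.14 weeks. Starting at a CR in week 12, 18 or 24 gives 36.14, 30.14 or 24.14 weeks, which is 6, 12 or 18 weeks less.

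**2. PR, never CR.** With PR at week 6 and progression at week 12, 24 or 48, the SAP gives 6.14, 18.14 or 42.14 weeks. Under the bulleted definition this patient has no objective improvement and would have no DOR.

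**3. Which Cohort 2 patients can record an on-study PR?** This depends on the reference sum. Suppose the sum was 100 mm before anti-PD-(L)1 therapy and 60 mm at study entry.

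| On-study sum (mm) | Change from 100 mm | If entry PR is carried forward | Change from 60 mm | If study baseline is the reference |
|---|---|---|---|---|
| 60 | −40.0% | PR | 0.0% | SD |
| 50 | −50.0% | PR | −16.7% | SD |
| 42 | −58.0% | PR | −30.0% | PR |
| 0 (taken as CR) | −100.0% | CR | −100.0% | CR |

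- *Study baseline.* Protocol 8.3.10.4 judges PR against the baseline sum, and SAP 3.1 takes baseline as the latest available assessment preceding first dose. Only patients with a further decrease of at least 30%, short of CR, are affected. A patient who holds the entry PR is SD and has no DOR. One who goes from SD directly to CR has the correct start.
- *Entry PR carried forward.* Protocol 11.1 and SAP 1.3.1 speak of conversion from PR to CR, which suggests that the entry status continues. An unchanged tumor would then be PR at the first scan and would start the clock.

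The mismatch exists on both readings and reaches more patients on the second.

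**4. Table 4, first row.** For "No baseline or unreadable baseline assessment, but readable post-baseline assessments" the table censors at first dose. PFS starts at first dose, so the same row works in Table 5. DOR starts later: with a response at day 43, the formula gives (1 − 43 + 1)/7 = −5.9 weeks.

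**The case against.** DOR is defined the same way in three places, as the duration of a CR or PR, and no sentence says that it measures the duration of objective improvement. The objective response rate is also summarized by cohort, so DOR could be meant to accompany that rate. This stands as a reading of the text, but neither document states it.

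The displayed Group 1 formula in SAP 3.11.2 counts every patient reaching CR or PR. Under that formula the PR-only patient is in the numerator and DOR matches it. This also stands: part of the conflict lies inside the primary endpoint, where formula and bullets disagree.

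Protocol 8.3.10.6 separately defines a duration of CR, which is close to what Cohort 2 needs. SAP 3.11.3 does not use it, and neither document assigns it to Cohort 2.

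A reader might infer several stronger things that the documents do not support:

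- *That the PR obtained on prior therapy starts the clock.* With that PR recorded 56 days before first dose, record 1 would give (210 + 56 + 1)/7 = 38.1 weeks, or 267/127 = +110%. But protocol 8.3.10.5 counts best response from the start of treatment, PR is judged against the baseline sum, and protocol 8.3.3 collects earlier measurements only as history. This reading is strained.
- *That every Cohort 2 patient is affected, or gets a DOR without any tumor shrinkage.* On the study-baseline reading neither is true.
- *That the combination is made to look more durable.* PR-only patients can shorten the median as well as lengthen it.
- *That negative durations will appear.* Without a readable baseline, a PR against baseline could hardly be assigned. Measurable disease and a baseline scan within 28 days are also required.

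**Conclusion.** The point holds in a limited form. As written, some Cohort 2 patients receive a DOR that starts before the objective improvement, and others receive one without meeting its bulleted definition. For a patient with PR then CR, the start can only lengthen DOR, by the PR-to-CR interval (6.0 weeks in the main illustration). The net effect on the Group 1 and overall median is not determinable, because PR-only patients can move it in either direction and the Cohort 2 size is not readable.

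The conclusion assumes that DOR should describe the response defined in the SAP 3.11.2 bullets. Its reach depends on the unsettled reference baseline: only further decreases of at least 30% short of CR if the study baseline applies, and unchanged tumors as well if the entry PR is carried forward. The first row of Table 4 is a drafting slip with little practical effect.

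**What to change.** - In SAP 3.11.3 and the Table 4 start date, limit DOR to patients with objective improvement. Start it at the first on-study scan meeting that definition: PR or CR for Cohorts 1, 3 and 4; CR for Cohort 2.
- State the reference baseline for on-study PR.
- Make the Group 1 numerator formula in SAP 3.11.2 agree with its bullets.
- Align protocol 8.3.10.6.
- As a minor tidy-up, change the first row of Table 4 to show that such patients are not in the DOR analysis.

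The cost is wording and one derivation. The downside is that fewer Cohort 2 patients contribute to DOR.
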